5.4 Dose Modifications

If subject requires that the study drug be discontinued because of an adverse event (as described below) or have a treatment interruption of greater than 8 weeks for olaparib or 8 weeks for durvalumab, at the investigator's discretion, they may continue on the other agent alone until progression. Refer to Appendix G and Appendix H for management of toxicities.

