5.4.1 Durvalumab Dose Modification

Dose reductions for durvalumab are not permitted. For dose modification and toxicity management guidelines for durvalumab, refer to Appendix G.

5.4.2 *Olaparib dose levels*

Dose Level	Olaparib
Level 0	300 mg BID
Level -1	250 mg BID
Level -2	200 mg BID
Level -3	Discontinue

Subjects requiring more than two dose reductions will have to discontinue olaparib. 100 mg and 150 mg tablets will be supplied for olaparib.

5.4.3 *Toxicities that require discontinuation from study treatment*

Protocol therapy should be discontinued if a subject experiences:

- Any CTCAE Grade 4 toxicity with the exception of:
 - CTCAE Grade 4 neutropenia of 5 days or fewer duration
 - CTCAE Grade 4 nausea/vomiting or diarrhea that resolves to Grade 3 or less within 72 hours
 - CTCAE Grade 4 laboratory abnormalities that can be readily corrected with 72 hours and do not result in hospitalization.
- CTCAE Grade 3 thrombocytopenia with hemorrhage
- CTCAE Grade 3 febrile neutropenia
- Hy's Law (AST or ALT >3x ULN with concomitant serum bilirubin >2x ULN and no alternate etiology)
- Bone marrow findings consistent with myelodysplastic syndrome (MDS)/acute myeloid leukemia (AML)

5.5 **Concomitant Medications and Supportive Care**

Because of the potential for drug-drug interaction, the concurrent use of all other drugs, over-the-counter medications, and alternative therapies must be documented on the eCRF.

Subjects should not donate blood while participating in this study or for at least 90 days following the last infusion of durvalumab or olaparib.

Refer to Appendix D for more information on concomitant medications and supportive care guidance.

5.6 **Other Concomitant Treatment**

Any medications, with the exceptions noted in Appendix D, which are considered necessary for the subject's welfare, and which it is believed will not interfere with the study medication, may be given at the discretion of the Investigator, providing the medications, the doses, dates and reasons for administration are recorded in the EDC.

In addition, any diagnostic, therapeutic or surgical procedure performed during the study period must be recorded in the EDC.

All medications (prescriptions or over-the-counter medications) continued at the start of the trial (from the time of informed consent) or started during the study or until 30 days from the end of the last protocol treatment and different from the study medication must be documented.

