Neutropenia and leukopenia	CTC Grade 3 or worse neutropenia occurs	
Manage as deemed appropriate by the investigator with close follow up and interruption of study drug. Primary prophylaxis with Granulocyte colony-stimulating factor (G-CSF) is not recommended, however, if a subject develops febrile neutropenia, study treatment should be stopped and appropriate management including G-CSF should be given according to local hospital guidelines. Please note that G-CSF should not be used within at least 24 h of the last dose of study treatment.
 
Study treatment can be restarted at the same dose if an AE of neutropenia or leukopenia have been recovered up to CTC AE Grade less than or equal to Grade 1 (ANC > 1.5 x 10⁹/L). Growth factor support should be stopped at least 24h before restarting study drug (7 days for pegylated G-CSF).
 
Any subsequent interruptions will require study treatment dose reductions to 250 mg BID as a first step and to 200 mg

		BID as a second step for a 300 mg monotherapy starting dose
Thrombocytopenia	CTCAE Grade 3 or worse	
Study treatment should be interrupted for a maximum of 4 weeks. In some cases, management of thrombocytopenia may require platelet transfusions. Platelet transfusions should be done according to local hospital guidelines.
 
Any subsequent interruptions will require study treatment dose reductions to 250 mg BID as a first step and to 200 mg BID as a second step for a 300 mg monotherapy starting dose

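### Appendix H gives two different olaparib doses for the first restart after Grade 3–4 neutropenia, and its restart rule is not aligned with the discontinuation list in Section 5.4.3

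*Combined protocol and SAP*

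**What the plan says.** Section 5.4.3 opens its list with "Protocol therapy should be discontinued if a subject experiences". The list includes "CTCAE Grade 3 febrile neutropenia", with no exception and no route back to treatment. It also includes any Grade 4 toxicity, apart from a few exceptions, one of which is "CTCAE Grade 4 neutropenia of 5 days or fewer duration". Grade 4 neutropenia that lasts longer than that is therefore a reason to discontinue.

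Section 5.4 tells sites: "Refer to Appendix G and Appendix H for management of toxicities".

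Appendix H deals with neutropenia in two main places:

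- **Nadir table.** For ANC below 1000/mm3 (Grade 3–4), olaparib is held and, once the toxicity is back to Grade 1, may go on at one dose level lower. A second such nadir leads to Level -2. A patient who needs more than two reductions stops olaparib.
- **Neutropenia and leukopenia row.** The trigger is "CTC Grade 3 or worse neutropenia occurs". The first instruction is "Manage as deemed appropriate by the investigator with close follow up and interruption of study drug". The row then says that "if a subject develops febrile neutropenia, study treatment should be stopped and appropriate management including G-CSF should be given". Its next paragraph says: "Study treatment can be restarted at the same dose if an AE of neutropenia or leukopenia have been recovered", meaning recovery to Grade 1 or better with ANC above 1.5 x 10^9/L. Growth factor must be off for at least 24 hours before restart (7 days if pegylated). Later interruptions bring the dose to 250 mg BID and then to 200 mg BID.

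**The concern.** Sites use these rules to decide whether a patient with severe neutropenia goes back on olaparib, and at what dose. If one appendix gives two doses for one event, two sites in this multi-center trial can treat the same patient differently, and both can point to the protocol. If the restart rule does not carve out the cases that 5.4.3 removes from treatment, a site working from the row could re-expose a patient after febrile neutropenia or prolonged Grade 4 neutropenia. What is at stake is patient safety and uniform dosing, not the efficacy test.

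**Working it through.** The plan states no figure on this point that could be reproduced. The check compares the texts, with simple dose arithmetic.

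**1. Do the nadir table and the neutropenia row cover the same event?** The row on prolonged hematological toxicities in Appendix H equates Grade 3 or worse neutropenia with ANC below 1 x 10^9/L. One litre is 10^6 mm3, so 10^9 / 10^6 = 1000/mm3. That is the nadir table's threshold. The recovery condition also matches (Grade 1 or better). The event and the trigger for restart are the same.

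**2. First restart dose from Level 0** (dose levels from Section 5.4.2):

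- Nadir table: Level -1 = 250 mg x 2 = 500 mg/day.
- Neutropenia row: same dose = 300 mg x 2 = 600 mg/day.
- Difference: 600 - 500 = 100 mg/day; 100 / 600 = 16.7%.

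No reading makes both correct.

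**3. Does the mismatch end there?** No. Starting at Level 0, with no reductions for other reasons:

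| Neutropenia event | Nadir table | Neutropenia row |
|---|---|---|
| First | 250 mg BID (500 mg/day) | 300 mg BID (600 mg/day) |
| Second | 200 mg BID (400 mg/day) | 250 mg BID (500 mg/day) |
| Third | third reduction, so stop (0 mg/day) | 200 mg BID (400 mg/day) |

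The row runs one step behind the table throughout, so the repair has to cover the whole sequence.

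**4. Section 5.4.3 beside the neutropenia row:**

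| Case | Section 5.4.3 | Neutropenia row |
|---|---|---|
| Grade 3 febrile neutropenia | discontinue protocol therapy | treatment stopped, G-CSF; restart rule follows with no febrile exclusion |
| Grade 4 neutropenia, more than 5 days | discontinue protocol therapy | within the row's scope; no duration limit on restart |

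For a Level 0 patient in either case, olaparib is 0 mg/day under 5.4.3 and could be 300 x 2 = 600 mg/day under the row.

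**5. Does any text settle which rule prevails?** Section 5.4 refers to Appendix H without ranking it. Appendix H does not mention 5.4.3; its only section reference is to 7.3. Appendix G says that it guides rather than mandates; Appendix H is titled as guidelines but has no such statement.

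**The case against.** The strongest reply is that 5.4.3 and the neutropenia row need not collide. Section 5.4.3 is specific, sits in the body of the protocol and is headed as a list that requires discontinuation, whereas the restart in the row is general and optional. A site that discontinues for febrile neutropenia breaches nothing in Appendix H. The row also uses a different verb for febrile cases (stopped) than for ordinary neutropenia (interruption), so restart may be meant to follow interruption only. And a general row that does not repeat the 5-day limit does not thereby cancel it.

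This largely stands. A reader might infer a flat contradiction over febrile neutropenia; the documents do not support that. They support an ambiguity. It remains because the row does not state the distinction, and because Appendix H writes of permanent discontinuation elsewhere (the anemia row) when it means a lasting stop. The G-CSF washout before restart does not decide the matter, since afebrile patients may also receive G-CSF.

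There are also real safeguards. Restart needs ANC above 1.5 x 10^9/L. An interruption of 2 weeks or more for severe neutropenia brings weekly counts and a smear, and counts still abnormal after 4 weeks bring hematology referral. A delay beyond 8 weeks ends olaparib. Section 5.7 lets the physician remove a patient for whom retreatment would be dangerous. These limit the harm but do not say which rule applies.

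None of this answers the dose clash inside Appendix H, which does not depend on what stopped means.

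**Conclusion.** The point holds in two parts of different strength. The first restart dose after ANC below 1000/mm3 is a flat contradiction within Appendix H: 500 against 600 mg/day from Level 0. The relation between 5.4.3 and the neutropenia row is an unresolved ambiguity with a plausible harmonised reading; at worst a Level 0 patient whom 5.4.3 removes is restarted at 600 mg/day.

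Two further inferences should be avoided. One is that the row also allows same-dose restart at 500 or 400 mg/day for patients at Level -1 or -2. That is true only if the earlier reductions had another cause, because the row requires a reduction at later interruptions. The other is that the toxicity stopping rule in Section 10.2 has the wrong probabilities. Its 0.11 and 0.89 are stated for assumed toxicity rates of 0.15 and 0.35 and do not depend on Appendix H. At most, which text a site follows could affect whether a given case is classed as requiring discontinuation and so counted.

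Severity is minor to moderate, as a safety clarification. The documents do not give the frequency of these events, so the number of patients affected cannot be estimated.

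**What to change.** Amend Appendix H in two places.

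1. Give one first restart dose after ANC below 1000/mm3 in both the nadir table and the neutropenia row. From Level 0, 250 mg BID is the more cautious of the two written doses. If it is chosen, the row's step-down sentence must move with it: 200 mg BID at the next event, then discontinuation, in line with the limit of two reductions.
2. Add to the neutropenia row: *Grade 3 or higher febrile neutropenia, and Grade 4 neutropenia lasting more than 5 days, require discontinuation of protocol therapy under Section 5.4.3 and olaparib is not restarted; any continuation of durvalumab alone follows Section 5.4. The restart rule below applies only to other neutropenia.*

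The added text should refer to protocol therapy, as 5.4.3 does. Naming olaparib alone would leave durvalumab unaddressed and create a new mismatch.

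The cost is a few lines in one protocol amendment, with no added visits, data or patients.

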5.7 Removing Subjects from the Protocol

In the absence of treatment delays because of adverse events, treatment will continue for 24 cycles or until one of the following criteria applies:

- Withdrawal by subject: subject decides to withdraw from the study
- Progressive disease. PSA progression during the treatment period is defined as a rising PSA confirmed on repeat measurement at least two weeks later and at a least 25% rise and 2 ng/mL above nadir or baseline, whichever is lower. The assessment for PSA progression that may lead to discontinuation while on treatment will not begin prior to Cycle 6 as ADT would not start until Cycle 5. PSA progression during the follow up period defined as PSA > 0.2 ng/mL confirmed by repeat measurement at least 2 weeks later.
- symptomatic disease progression at any time
- objective clinical disease progression
- Intercurrent illness that prevents further administration of treatment, including bone marrow findings consistent with myelodysplastic syndrome (MDS)/acute myeloid leukemia (AML)
- Adverse event: unacceptable adverse event(s) that may or may not be directly related to treatment but that, in the judgment of the treating physician, makes it dangerous for the subject to be retreated
- Physician decision: general or specific changes in the subject's condition that render the subject unacceptable for further treatment, in the judgment of the investigator

Because an excessive rate of withdrawals can render the study uninterpretable, unnecessary withdrawal of subjects should be avoided. When a subject discontinues treatment early, the investigator should make every effort to contact the subject and to perform a final evaluation. The reason(s) for withdrawal should be recorded.

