2.3 Exploratory Objectives

To determine:

- Undetectable PSA at 11 months (cycle 11) (irrespective of testosterone level)
- Time to PSA progression defined as the time to PSA increase that is $\geq 25\%$ and $\geq 2\text{ng/mL}$ above the nadir, and which is confirmed by a second value > 3 weeks later
- Change in PSA doubling time at 24 months relative to PSA doubling time from the first dose of study drug (using the last 3 values from each time point)
- Comparison of Patient Reported Outcome (PRO) assessments of toxicity (PRO-CTCAE) to clinician reported toxicity assessments (CTCAE v.5.0)
- Changes in immune biomarkers with treatment. Peripheral blood mononuclear cells (PBMCs) will be collected that can later be analyzed for the immunomodulatory effects of the regimen by measuring for example, discrete T-cell populations. Archival tissue will also be analyzed for immune-related genes that may associate with response.

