3.1.2 Males 18 years of age and above

3.1.3 Body weight $> 30\text{kg}$

3.1.4 History of radical prostatectomy and/or primary radiation therapy to the prostate

3.1.5 Histologically confirmed prostate cancer with progressive disease defined as:

- Rising PSA (50% or more increase to a level of 0.50 ng/mL or more, based on at least 3 PSA determinations obtained at least 1 week apart). The 50% rise in PSA is across the 3 determinations, and these determinations do not need to be sequential.
- PSA doubling time of \leq 9months as calculated according to the Memorial Sloan Kettering Cancer Center nomogram
(<http://www.mskcc.org/mskcc/html/10088.cfm>)

3.1.6 No evidence of metastatic disease on conventional imaging (CT/MRI and bone scan). However, subjects with pelvic and/or retroperitoneal nodes $< 2\text{cm}$ in the short axis will be permitted on study, as they are considered not to have definitive metastases. (Note: *Metastatic disease on investigational imaging, Prostate Specific Membrane Antigen-targeted (PSMA) PET, PET-choline, or other novel PET tracers who do not have evidence of metastatic disease using conventional imaging (CT/MRI, bone scan) are allowed.*)

3.1.7 Molecular evidence of DDR deleterious mutations (somatic or germline), including BRCA1, BRCA2, ATM, CHEK1, CHEK2, FANCA, RAD51B, RAD51C, RAD51D, RAD54L, PALB2, BRIP1, BARD1, or CDK12. Mutations may be truncating, splice site mutations, missense or homozygous deletions. Mutation status is determined by a local laboratory with the result documented in the subject's medical record, previously obtained genomic testing from a CLIA-certified lab, or via archival or fresh tissue.

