3.2 Exclusion Criteria

- 3.2.1 No other malignancy from which the subject has been disease-free for less than 3 years, with the exception of adequately treated and cured non-invasive malignancies such as basal or squamous cell skin cancer or superficial bladder cancer.
- 3.2.2 Less than one month prior to treatment start from last prior regimen or radiation exposure. Prior radiotherapy to the prostate (adjuvant or salvage radiotherapy) is allowed.
- 3.2.3 No prior investigational use with an anti-PD(1) including durvalumab or anti-CTLA4 antibody.
- 3.2.4 No prior treatment with a PARP inhibitor, including olaparib.
- 3.2.5 No concomitant or prior therapy with any of the following: IL-2, interferon, or other non-study immunotherapy regimens; immunosuppressive agents; or chronic use of systemic corticosteroids within 6 weeks of treatment start. Exceptions include: intranasal, inhaled, topical steroids, or local steroid injections (e.g., intra articular injection); Systemic corticosteroids at physiologic doses not to exceed 10 mg/day of prednisone or its equivalent; Steroids as premedication for hypersensitivity reactions (e.g., CT scan premedication)
- 3.2.6 No receipt of live attenuated vaccine within 30 days prior to treatment start *Note: enrolled subjects should not receive live vaccine while receiving IP and up to 30 days after the last dose of study therapy*
- 3.2.7 Concomitant use of known strong CYP3A inhibitors (e.g., itraconazole, telithromycin, clarithromycin, protease inhibitors boosted with ritonavir or cobicistat, indinavir, saquinavir, nelfinavir, boceprevir, telaprevir) or moderate CYP3A inhibitors (e.g. ciprofloxacin, erythromycin, diltiazem, fluconazole, verapamil). The required washout period prior to treatment start is 2 weeks.
- 3.2.8 Concomitant use of known strong (e.g., phenobarbital, enzalutamide, phenytoin, rifampicin, rifabutin, rifapentine, carbamazepine, nevirapine and St John's Wort) or moderate CYP3A inducers (e.g., bosentan, efavirenz, modafinil). The required washout period prior to starting olaparib is 5 weeks for enzalutamide or phenobarbital and 3 weeks for other agents.

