5. TREATMENT/INTERVENTION PLAN

This is a phase II, single arm, multi-center trial that will evaluate the combination of olaparib 300mg twice daily (600mg total daily dose) with durvalumab 1500mg IV monthly in biochemically recurrent castration sensitive prostate cancer. The trial will be conducted at sites who are members of the PCCTC Network.

As seen in the trial design (Figure 2), subjects will be treated concurrently with olaparib + durvalumab continuously for 24 months. After the first 4 months, if a subject fails to achieve an undetectable PSA with the combination of olaparib and durvalumab, ADT will be added for 6 months (starting at Cycle 5) while continuing treatment with olaparib and durvalumab. For subjects who have an undetectable PSA [PSA of <0.05 or PSA <0.10] for institutions where this is the lower limit of detection] after the first 4 months of treatment, they will continue on the combination of olaparib + durvalumab continuously for 24 months (without ADT). As long as it is believed that subjects are clinically benefiting, they will remain on treatment for up to 24 months with olaparib and durvalumab. For example, a subject with a PSA reduction that does not achieve an undetectable PSA would be allowed to remain on study for the duration of the trial. Subjects who meet progression criteria while on active therapy would come off of trial. If subjects respond and later progress in the one-year follow-up period (beyond 24 months), they will be allowed to be re-induced with the combination.

Figure 2. Study schema for olaparib and durvalumab in subjects with castration-sensitive prostate cancer (biochemical recurrence) harboring DNA damage repair mutations

DDR deleterious mutations (somatic or germline) will include BRCA1 (breast cancer susceptibility gene), BRCA2, ATM (ataxia telangiectasia mutated serine/threonine kinase), CHEK2, FANCA, RAD51C, RAD51D, PALB2, BRIP1, BARD1, and CDK12. Mutations may be truncating, splice site mutations, missense or homozygous deletions. Subjects will be allowed on trial using local testing, previously obtained genomic testing from a validated lab (e.g., expedited germline testing from Color), or via archival or fresh tissue.

The following assessments and procedures will occur during the study. A schedule of assessments is provided in Appendix B.

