8. CRITERIA FOR OUTCOME ASSESSMENT/THERAPEUTIC RESPONSE

8.1 Therapeutic Response

8.1.1 PSA

This trial will measure PSA monthly for the first 24 months. The primary endpoint is an undetectable PSA at 24 months with non-castrate levels of testosterone (>150 ng/dL).

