10.5 Statistical Procedures and Analysis

Summary statistics include the number of observations, mean, standard deviation, median, minimum, and maximum values.

Statistical methods for the analyses

An exact binomial test will be used to evaluate the efficacy of the 24 months undetectable PSA endpoint. In addition, the proportion of subjects that attain an undetectable PSA at (1) 5 months, (2) 11 months, and (3) 24 months will be computed along with their attendant 95% confidence intervals. The probability of PSA progression over time will be estimated using the cumulative incidence function.

A paired t-test will be used to compare the PSA doubling time at 24 months to the PSA doubling time at study entry.

Kendall's tau with longitudinal data will be used to compare patient recorded toxicities to physician recorded toxicities over time.

The immunologic profile of patients over time will be described using nonparametric kernel smoothing.

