- q. A blood or saliva sample will be collected during screening as matched normal for sequencing for patients completing prospective Next Generation Sequencing using assays that require a matched normal sample.
- r. Subjects will be treated concurrently with olaparib + durvalumab continuously for 24 months. Durvalumab will be administered on Day 1 of each cycle (± 3). After the first 4 months, if a subject fails to achieve an undetectable PSA [PSA of <0.05 (or PSA <0.10 for institutions where this is the lower limit of detection) with the combination of olaparib and durvalumab, ADT will be added for 6 months (starting at Cycle 5) while continuing treatment with olaparib and durvalumab (see section 6.3 for additional details regarding ADT). For subjects who have an undetectable PSA after the first 4 months of treatment, they will continue on the combination of olaparib + durvalumab continuously for 24 months (without ADT). As long as it is believed that subjects are clinically benefiting, they will remain on treatment for up to 24 months with olaparib and durvalumab. For example, a subject with a PSA reduction that does not achieve an undetectable PSA would be allowed to remain on study for the duration of the trial. Subjects who meet progression criteria while on active therapy would come off of trial.
- s. Subjects who have an undetectable PSA after completion of protocol therapy will be followed every 12 weeks. PSA, CMP, CBC, and TFTs should be performed. A physical exam will be performed. Subjects who respond and later progress in the first year following the 24 month treatment phase will be allowed to re-induce with the combination and will restart their calendar with C1D1 if they continue to meet all clinical eligibility criteria are met. PCCTC must review the confirmation of eligibility prior to re-inducing treatment.

APPENDIX C. ACTIONS REQUIRED IN CASES OF COMBINED INCREASE OF AMINOTRANSFERASE AND TOTAL BILIRUBIN – HY'S LAW

Introduction

This Appendix describes the process to be followed in order to identify and appropriately report cases of Hy's Law. It is not intended to be a comprehensive guide to the management of elevated liver biochemistries. Specific guidance on the managing liver abnormalities can be found in Appendix H and Appendix I of the protocol.

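### Does the lower PSA threshold used in follow-up (5.7) leave the exploratory PSA-progression endpoint without a usable definition?

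*Combined protocol and SAP*

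**What the plan says.** Section 2.3 lists time to PSA progression among the exploratory objectives and defines it there: a PSA increase of at least 25% and at least 2 ng/mL above nadir, "which is confirmed by a second value > 3 weeks later". It sets no start and no end to the period.

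Section 5.7 gives criteria for taking subjects off protocol. On treatment, progression needs a 25% rise and 2 ng/mL above the lower of nadir and baseline. It is confirmed at least two weeks later and is not assessed for discontinuation before Cycle 6. After treatment the rule changes: "PSA progression during the follow up period defined as PSA > 0.2 ng/mL confirmed by repeat measurement at least 2 weeks later".

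Section 10.1.4 lists the endpoint only as PSA PFS. Section 10.5 says "The probability of PSA progression over time will be estimated using the cumulative incidence function". Neither points to 2.3 or 5.7, gives a time horizon or names a competing event.

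On timing, Section 8.1.1 says "This trial will measure PSA monthly for the first 24 months", and Appendix B note s says "Subjects who have an undetectable PSA after completion of protocol therapy will be followed every 12 weeks". On re-treatment, Section 5 says of responders that if they "later progress in the one-year follow-up period (beyond 24 months), they will be allowed to be re-induced". Note s makes this conditional on still meeting the clinical eligibility criteria. Those might include 3.1.5 ("Rising PSA (50% or more increase to a level of 0.50 ng/mL or more") and, read literally, 3.2.3 on prior durvalumab and 3.2.4 ("No prior treatment with a PARP inhibitor, including olaparib").

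**The concern.** One term carries two meanings in follow-up, and the statistical section does not choose between them. Under 2.3, a man whose PSA was undetectable at the end of treatment could be called progressed by 5.7, perhaps even re-treated, and still count as event-free. The response would then look more durable than the protocol's own follow-up rule says it was. The protocol's rationale (1.3.1) rests heavily on durable undetectable PSA, and with 32 men in a single arm a choice of definition made after seeing the data could change how durability is described. Re-treatment before a 2.3 event could also prevent that event, and no handling is given. The change of label from time to PSA progression to PSA PFS leaves it open whether death is an event or a competing risk.

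**Working it through.** **1. The plan's own figure.** Section 10.2: n = 32, active if at least 8 successes, rates 0.15 and 0.35, one-sided size 0.10, power above 0.90. Exact binomial: P(X ≥ 8 | 0.15) = 0.0958 and P(X ≥ 8 | 0.35) = 0.918. Both agree with the plan. Neither uses a PSA-progression definition, and the 0.2 ng/mL rule starts only after the month-24 assessment.

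**2. Distance between the follow-up thresholds.** The nadir is taken as the detection limit in 10.1.1 (0.05, or 0.10 at some sites). The 2.3 threshold is max(1.25 × nadir, nadir + 2).

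| | Nadir 0.05 | Nadir 0.10 |
|---|---|---|
| 2.3 threshold (ng/mL) | 2.05 | 2.10 |
| Ratio to 0.2 | 10.25 | 10.5 |
| Doublings from 0.2, log2(ratio) | 3.358 | 3.392 |
| Lag at doubling time 3 / 6 / 9 months | 10.1 / 20.1 / 30.2 months | 10.2 / 20.4 / 30.5 months |

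**3. Who is discordant within the follow-up year.** Assumption: exponential regrowth from the detection limit, starting at month 24. The documents give no regrowth rate. Their only benchmark is the entry doubling time of at most 9 months (3.1.5).

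- Limit 0.05: the 0.2 rule is met within 12 months if the doubling time is at most 12 / log2(0.20/0.05) = 12/2.000 = 6.0 months. The 2.3 rule is met if it is at most 12 / log2(2.05/0.05) = 12/5.358 = 2.2. The discordant range is about 2.2 to 6.0 months.
- Limit 0.10: 12/1.000 = 12.0 and 12/4.392 = 2.7. The range is about 2.7 to 12.0 months, and its upper end exceeds the 9-month benchmark.
- If only scheduled 12-weekly values confirm, the first qualifying value must fall by week 36, or 36 × 7 / 30.4375 = 8.28 months. The upper ends become 8.28/2.000 = 4.1 and 8.28/1.000 = 8.3; the lower ends become 8.28/5.358 = 1.5 and 8.28/4.392 = 1.9.

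**4. Re-induction before a 2.3 event.** If 3.1.5 applies, PSA must reach 0.50. The upper ends within 12 months become 12 / log2(0.50/0.05) = 12/3.322 = 3.6 months, and 12 / log2(0.50/0.10) = 12/2.322 = 5.2 months. If 3.2.3 and 3.2.4 apply as written, nobody is re-induced and this route is empty.

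**5. The treatment period.** Scheduled visits 28 days apart, each ±3 days, lie 22 to 34 days apart, so a scheduled repeat meets both confirmation rules. The Cycle 6 start still separates the rules. Illustration (assumed): baseline 5 ng/mL, doubling time 5 months, no initial fall.

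- C4D1: day 84 after C1D1 = 2.76 months, PSA = 5 × 2^(2.76/5) = 7.3, a rise of 47% and 2.3 ng/mL.
- C5D1: day 112 = 3.68 months, PSA = 5 × 2^(3.68/5) = 8.3.

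That is a confirmed 2.3 event which 5.7 does not assess, and ADT is then added at Cycle 5. Here 2.3 is the stricter rule, so the discordance runs both ways and stopping the analysis at month 24 would not remove it.

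**6. Effect on the curve.** With no earlier censoring, each discordant man shifts the cumulative incidence by 1/32 = 3.1 points. How many there would be cannot be derived from the documents.

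**The case for a change.** The best case for a change does not depend on the growth assumptions. The 0.2 rule applies after treatment has ended, so it cannot be a stopping rule for the 24 cycles; it is the protocol's only stated meaning of progression in follow-up. Section 10 also drops the 2.3 endpoint name, so an analyst who took 5.7 for the follow-up part would not be contradicting Section 10. Even if 2.3 governs, the plan is silent on a man re-treated before a 2.3 event.

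The factual part stands: the definitions differ, Section 10 cites neither, and horizon, competing event and re-treatment are unstated. It does not follow that the endpoint is undefined. Section 2.3 names the endpoint and defines it in the same sentence; 5.7 sits in the removal section and never claims to define an endpoint; 10.5 uses the term that 2.3 defines. Cumulative incidence already implies a competing event, and death without progression is the obvious one.

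The natural repair, counting whichever of the two rules is met first, is open to dispute. Its threshold would fall about tenfold at month 24, and note s provides follow-up for men whose PSA is undetectable after therapy. A best responder who reaches a confirmed 0.21 would count as progressed, while a man who ends treatment at a stable 1.0 would not. The single 2.3 rule avoids that step. Its cost is a later event for slow regrowth after month 24, which is a fair trade-off.

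**Conclusion.** No change to the plan follows. What is missing is detail on an exploratory, unpowered endpoint, and an analyst would fill it sensibly: 2.3 as the event definition, death without progression as the competing event, the horizon stated in the report, and any post-month-24 portion described as resting on the men still followed. A description of progression under 5.7 in follow-up can be added from PSA values already collected.

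The follow-up gap is about 3.4 doublings, assuming regrowth from the detection limit. Each discordant man moves the curve by about 3 points, in either direction depending on the period. The number of such men is unknown, and the re-treatment concern may be void under 3.2.3 and 3.2.4. The primary test keeps its exact size of 0.0958 and power of 0.918.

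Separately from the analysis, Section 5, 5.7, note s and exclusions 3.2.3 and 3.2.4 do not sit together on progression and re-induction. Reconciling them is a clinical matter for the sponsor; no view is taken here on which rule is right, and the conclusion above does not depend on it.
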